STUDY DESIGN	
Structure
 
Main study cohort: Prospective, multi-center, single-arm, open label, enrolling a total of 129 patients referred to surgical creation of new brachiocephalic fistula (BCF). The VasQ will be applied to the AV fistula in all patients. The primary effectiveness endpoint for this trial will be measured at 6 months and compared to a performance goal (PG). Safety will compare descriptively between AE rates for Steal, Infection, Aneurysm and Seroma. Patients will be followed up for an additional 18 months for a total of 2 years. Additionally, this trial has several secondary endpoints.
 
Supplementary study cohort: A total of 15 patients will be prospectively enrolled which are referred to surgical creation of a new forearm arteriovenous fistula. VasQ will be applied to the AV fistula in all patients. Patients will be followed in the same manner as in the Main study cohort, however, the data will be reported separately and also included in the secondary [REDACTED] analysis.
 
Duration
 
Primary endpoint is defined at 6 month post index procedure of fistula placement. Patients will be further followed up to 2 years post index procedure.
 
Visit schedule
 
Screening – per eligibility criteria.
 
Index fistula procedure – VasQ implantation.
 
1, 3 months - Doppler US; Clinical examination, SAE follow up; Dialysis status; Access interventions.
 
6 months – Primary endpoint, Doppler US; Clinical examination, SAE follow up; Dialysis status; Access interventions.
 
9 months – Phone call; SAE follow up; Dialysis status.
 
12 months – Doppler US; clinical examination; X-ray imaging of the arm; SAE follow up; Dialysis status; Access interventions.
 
24 months - Doppler US; clinical examination; X-ray imaging of the arm; SAE follow up; Dialysis status

Document title:
VasQ FDA pivotal Protocol

Document No.
CD0121

Revision
12.0
14 March 2021

Page
6 of 42

ENDPOINTS

Primary effectiveness endpoint:

Primary patency rate at 6 months post AVF creation

1 = Success = Intervention free access patency and flow ≥ 500 ml/min determined by Doppler ultrasound.

0 = Failure = Access occluded or flow < 500 ml/min determined by Doppler ultrasound.

The success rate on this primary endpoint will be compared to a PG of 55.0%.

Secondary [REDACTED] analysis:

Primary patency rate at 6 months post AVF creation as defined for the primary effectiveness endpoint, calculated for the main and supplementary cohorts (upper arm and forearm fistula) combined.

The success rate on this [REDACTED] analysis will be compared to a PG of 55.0%.

Safety

The main safety endpoints are occurrence of the following non-thrombotic safety events at up to 6 months: Steal, Infection, Aneurysm, Seroma. Each of these endpoints will be scored dichotomously for each subject as

0 = did not occur

1 = occurred

Thus, for the main safety analyses this study will have 4 rates assessing safety—one for each of the events enumerated.

COHORT

Sample size

144 subjects will be enrolled in this trial in the US.

1. 129 will be enrolled in the main cohort
2. 15 will be enrolled in the supplementary cohort

Inclusion criteria

1. Main study cohort: Patients referred for creation of a new brachiocephalic fistula who consent to take part in the study and which are not indicated for a more distal fistula per treatment guidelines.
Supplementary study cohort: Patients referred for creation of a new forearm fistula who consent to take part in the study.
2. Male and female participants.
3. Age 18-80 years.
4. Patients willing and able to attend follow up visits over a period of 24 months.

Exclusion criteria

Document title: VasQ FDA pivotal Protocol	Document No. CD0121	Revision 12.0 14 March 2021	Page 7 of 42
--	------------------------	-----------------------------------	-----------------

1. Patients with the planned index procedure being a revision surgery of an existing fistula.
2. Main study cohort: Target artery smaller than 2.5 mm or larger than 6 mm in inner diameter by preoperative ultrasound.
Supplementary study cohort: Target artery smaller than 2 mm or larger than 4.1 mm in inner diameter by preoperative ultrasound.
3. Main study cohort: Target vein smaller than 2.5 mm in inner diameter by preoperative ultrasound.
Supplementary study cohort: Target vein smaller than 2 mm in inner diameter by preoperative ultrasound.
4. Significantly stenotic target vein on the side of surgery ($\geq 50\%$) as diagnosed on preoperative ultrasound. (Scan should include the area between the planned anastomosis site and the Axillary vein.)
5. Unusual anatomy or vessel dimensions (observed on pre-operative ultrasound or intraoperatively) and which preclude adequate fit of the VasQ.
6. Patients with central venous stenosis or obstruction on the side of surgery.
7. Depth of vein greater than 8 mm (on ultrasound) on side of surgery.
8. Known coagulation disorder.
9. Congestive heart failure NYHA class ≥ 3 .
10. Prior steal on the side of surgery.
11. Known allergy to nitinol.
12. Life expectancy less than 30 months.
13. Patients expecting to undergo kidney transplant within 6 months of enrollment.
14. Women of child bearing age without documented current negative pregnancy test.
15. Inability to give consent and/or comply with the study follow up schedule.

**TERMS AND
DEFINITIONS**

AE – Adverse event
 AV – Arteriovenous
 AVF – Arteriovenous fistula
 BCF – Brachiocephalic fistula
 CRF – Case report form
 CTA – Clinical trial agreement
 eCRF – Electronic case report form
 ESRD – End stage renal disease
 FAS – Full analysis set
 GLMM - Generalized linear mixed model
 ICH-GCP - International Conference on Harmonization - Good Clinical Practice
 IDE – Investigational device exemption

Document title: VasQ FDA pivotal Protocol	Document No. CD0121	Revision 12.0 14 March 2021	Page 8 of 42
--	------------------------	-----------------------------------	-----------------

IFU – Instructions for use
 IRB – Institutional review board
 KDOQI – Kidney disease outcomes quality initiative
 MAR – Missing at random
 MMI- Medical Metrics Inc.
 PG –Performance goal
 PP – Per protocol
 SAE – Serious adverse event
 SOP – Standard operating procedure
 TTFM – Transit time flow measurement
 UADE – Unanticipated adverse device effect
 US - Ultrasound
 USA – United States

1 SCOPE AND PURPOSE

This document describes a prospective clinical study of the Laminate VasQ external support for arteriovenous fistulas. The VasQ constraints and directs the geometrical parameters of the fistula, such as the anastomosis radius of curvature as well as the vascular diameter and gradient in the vicinity of the AV fistula. These geometrical constraints direct flow and influence hemodynamics with the intent to minimize turbulence and promote laminar flow. The device is designed to improve fistula outcomes. The VasQ is intended for use as an external support for autologous vascular conduits created by means of vascular surgery, where veins are incorporated into the arterial circulation for purposes such as vascular access.

2 BACKGROUND AND RATIONALE

2.1 The clinical need

Vascular access continues to be a leading cause for hospitalization and morbidity in patients with chronic kidney disease. Appropriate care of hemodialysis patients requires constant attention to the maintenance of vascular access patency and function. An ideal access delivers a flow rate to the dialyzer adequate for the dialysis prescription, has a long use-life, and has a low rate of complications (e.g., infection, stenosis, thrombosis, aneurysm, repeat interventions, and limb ischemia). Of available accesses, the surgically created fistula comes closest to fulfilling these criteria.

The AV fistula is created by suturing together an artery and a vein, usually in the arm below the elbow (brachio-cephalic) or above the wrist (radio-cephalic), and allowing arterial pressure to enlarge the vein to accommodate a large needle. In order to be used for dialysis, a newly created fistula must maintain patency and mature; that is, the artery and vein must undergo dilation and remodeling to accommodate the markedly increased blood flow that results from creating the AV anastomosis.

Document title:
VasQ FDA pivotal Protocol

Document No.
CD0121

Revision
12.0
14 March 2021

Page
9 of 42

Studies over several decades consistently demonstrate that native fistula accesses have the best 4- to 5-year patency rates and require the fewest interventions compared with other access types. However, despite the clear benefits of native arteriovenous (AV) fistulas over other access methods, early failure occurs in over 40% of these fistulas. Most of these failures occur in the peri-anastomotic region.

Local flow patterns and exposure of the vein to arterial pressures and high flow trigger the onset of remodeling and intimal hyperplasia. As demonstrated in the literature, placing a venous external support has the potential to reduce wall shear stress, radial force and cyclic stretching of medial and endothelial cells, all of which might be expected to reduce intimal hyperplasia (wall thickening). In addition, control of the geometric configuration as well as hemodynamic and flow patterns also has the potential to decrease damaging turbulent flow near the anastomosis region, and hence decrease the fistula's early maturation failure rate.

2.2 The VasQ

The VasQ, an external support device for AV fistula, is implanted by the vascular surgeon during the fistula creation surgical procedure. The VasQ targets those segments of the vein which are immediately proximal and distal to the anastomosis, where flow disturbances and intimal hyperplasia are most significant and where frequent occlusions occur.

VasQ is a Nitinol implant (Figure 2-1), which incorporates a conical braided wire portion (around the vein), welded to laser cut tube (around the anastomosis). The VasQ is available in 4 dimensions so as to best comply with vessel diameters and ensure optimal fit with the fistula.

[figure not shown]

Figure 2-1: VasQ as positioned over the fistula

2.2.1 Intended use

The VasQ is intended for use as an external support for upper extremity arteriovenous fistulas created for vascular access by means of vascular surgery.

Document title:
VasQ FDA pivotal Protocol

Document No.
CD0121

Revision
12.0
14 March 2021

Page
10 of 42

2.2.2 Accessories

An accessory to the VasQ device is the dedicated Selection Tool, which is used during the procedure to gage the artery diameter and select the best fitting VasQ model.

3 STUDY OBJECTIVES

The study is designed to clinically demonstrate safety and effectiveness of the VasQ in the following aspects:

1. Demonstrate the potential of the VasQ in meeting the specified performance goal in primary patency of AV fistulas.
2. Demonstrate the safety of the VasQ in vascular access.

4 STUDY DESIGN

4.1 Structure

This is a prospective, multi-center, single-arm, open label study enrolling patients in the US, who are referred for creation of a new AV fistula. The VasQ will be applied to the AV fistula in all patients. The primary effectiveness endpoint for this trial will be measured at 6 months and compared to a performance goal (PG). Patients will be followed up for an additional 18 months for a total of 2 years. Additionally, this trial has several secondary endpoints. 129 patients will be enrolled with upper arm fistulas + 15 patients with forearm fistulas.

4.2 Visit schedule

Screening – per eligibility criteria

Index fistula procedure – VasQ implantation in all subjects

- 1 month – [REDACTED]
- 3, 6 months – [REDACTED]
- 9 months – [REDACTED]
- 12 months – [REDACTED]
- 24 months – [REDACTED]

4.3 Study flow diagram

[figure not shown]
See following page for the study flow diagram.

Document title:
VasQ FDA pivotal Protocol

Document No.
CD0121

Revision
12.0
14 March 2021

Page
11 of 42

Document title: VasQ FDA pivotal Protocol	Document No. CD0121	Revision 12.0 14 March 2021	Page 12 of 42
--	------------------------	-----------------------------------	------------------

5 STUDY POPULATION

5.1 Number of patients

A total of 129 subjects will be enrolled in the main study cohort in up to 17 US sites. Individual enrollment site will be limited to 20% of the cohort (25 subjects).

15 additional subjects undergoing forearm fistula creation will be enrolled in a supplementary study cohort.

5.2 ELIGIBILITY CRITERIA

5.2.1 Inclusion criteria:

1. Main study cohort: Patients referred for creation of a new brachiocephalic fistula who consent to take part in the study and which are not indicated for a more distal fistula per treatment guidelines.
Supplementary study cohort: Patients referred for creation of a new forearm fistula who consent to take part in the study.
2. Male and female participants.
3. Age 18-80 years.
4. Patients willing and able to attend follow up visits over a period of 24 months.

5.2.2 Exclusion criteria:

1. Patients with the planned index procedure being a revision surgery of an existing fistula.
2. Main study cohort: Target artery smaller than 2.5 mm or larger than 6 mm in inner diameter by preoperative ultrasound.
Supplementary study cohort: Target artery smaller than 2 mm or larger than 4.1 mm in inner diameter by preoperative ultrasound.
3. Main study cohort: Target vein smaller than 2.5 mm in inner diameter by preoperative ultrasound.
Supplementary study cohort: Target vein smaller than 2 mm in inner diameter by preoperative ultrasound.
4. Significantly stenotic target vein on the side of surgery ($\geq 50\%$) as diagnosed on preoperative ultrasound. (Scan should include the area between the planned anastomosis site and the Axillary vein.)
5. Unusual anatomy or vessel dimensions (observed on pre-operative ultrasound or intraoperatively) and which preclude adequate fit of the VasQ.
6. Patients with central venous stenosis or obstruction on the side of surgery.
7. Depth of vein greater than 8 mm (on ultrasound) on side of surgery.
8. Known coagulation disorder.
9. Congestive heart failure NYHA class ≥ 3 .
10. Prior steal on the side of surgery.
11. Known allergy to nitinol.

Document title: VasQ FDA pivotal Protocol	Document No. CD0121	Revision 12.0 14 March 2021	Page 13 of 42
--	------------------------	-----------------------------------	------------------

12. Life expectancy less than 30 months.
13. Patients expecting to undergo kidney transplant within 6 months of enrollment.
14. Women of child bearing age without documented current negative pregnancy test.
15. Inability to give consent and/or comply with the study follow up schedule.

5.3 Relevance to Medicare beneficiaries

The cohort eligible for participation in this study are all patients with ESRD who require vascular access for administration of dialysis. ESRD patients of any age who are receiving dialysis are all eligible for Medicare within certain timing rules. Hence it is expected that all of patients participating in this study are either already Medicare beneficiaries or are eligible to become beneficiaries within several months after enrollment into the study.

6 ENDPOINTS

6.1 Primary effectiveness endpoint

The primary effectiveness endpoint is primary patency at 6 months post AVF creation. Fistulas are defined as primarily patent¹ if they are free from any intervention up to 180 days (endovascular or surgical) to maintain or restore blood flow and demonstrate minimum flow on Doppler or palpable thrill and audible bruit or are receiving dialysis through the fistula.

- The flow criterion is adapted to a range consistent with a documented² interobserver and intraobserver variability, with various ultrasound systems.
- Due to the COVID-19 pandemic, patients are more prone to miss their on-site doppler examination at 6 months, but still undergo access site assessment (i.e. thrill palpation and bruit evaluations) which is a valid assessment for confirmation of patency (Shenoy et al.). Thus, patients that have bruit and thrill data indicating patency or actively receiving dialysis through the fistula at 6 months without interventions, will be considered as success.

1 = Success = Intervention free access patency at 180 days. Confirmation of fistula patency is established by meeting one of the following three conditions:

1. Artery or vein flow ≥ 500 (-50) ml/min determined by Doppler ultrasound.
or
2. Clinical assessment of palpable Thrill and audible bruit at 6 months
or
3. Patient is receiving dialysis through the fistula at 6 months

Note: if patient is not receiving dialysis through the fistula at 6 months, this will not indicate failure.

0 = Failure = Access underwent intervention before 180 days
or

¹ Shenoy, Surendra, et al. "Clinical trial end points for hemodialysis vascular access: background, rationale, and definitions." Clinical Journal of the American Society of Nephrology 13.3 (2018): 490-494.

² Hoyt Kenneth et al. Accuracy of Volumetric Flow Rate Measurements. An In Vitro Study Using Modern Ultrasound Scanners. J Ultrasound Med 2009; 28:1511–1518

Document title: VasQ FDA pivotal Protocol	Document No. CD0121	Revision 12.0 14 March 2021	Page 14 of 42
--	------------------------	-----------------------------------	------------------

None of the following conditions are met at 180 days:

- Flow \geq 500 (-50) ml/min
- Thrill is palpable and bruit is audible
- Patient is receiving dialysis through the fistula

6.2 Safety endpoints

6.2.1 Main safety endpoints

The main secondary endpoints in this trial are, for each subject, occurrence of the following clinically meaningful safety events at up to 6 months:

- Steal
- Infection
- Aneurysm
- Seroma

These four safety endpoints have been selected since they are the major non-thrombotic access site complications associated with fistulas. Thrombotic complications which affect maturation and patency will be covered in this trial by the primary and secondary effectiveness endpoints.

These endpoints, which are defined in Section 6.4, will be scored dichotomously for each subject as 0 (did not occur) or 1 (occurred); i.e. each subject is scored 0 or 1 on each of the four endpoints. Additionally, the cumulative number of events over all subjects will be computed. This will allow both detailed and general comparisons to the relevant literature.

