Document title:
VasQ FDA pivotal Protocol

Document No.
CD0121

Revision
12.0
14 March 2021

Page
23 of 42

- [REDACTED]
[REDACTED]
- [REDACTED]
[REDACTED]
[REDACTED]
[REDACTED]
- [REDACTED]
[REDACTED]
 - A de-identified DICOM file of the US scan will be uploaded to a central system provided by Medical Metrics Inc. (MMI). Instructions for submitting images to MMI are provided in the Image Transfer Protocol and section 11.3.
- Physical examination including:
 - Palpation for thrill.
 - Listening for bruit by stethoscope.
 - Documentation of non-thrombotic access events: steal, infection, aneurysm, and seroma (per definitions in section 6.4).
- X-ray imaging of the arm to determine VasQ integrity. [REDACTED]
[REDACTED]
[REDACTED]
[REDACTED]
[REDACTED]
[REDACTED]
[REDACTED]
- Dialysis status (start/stop dates, dialysis access, flows, number and length of weekly sessions).
- Document any access intervention (type, date, purpose [initiating vs. maintenance of dialysis], outcome).
- Adverse events / Serious Adverse Events will be recorded in accordance with section 8.
- Concomitant medications update will be recorded in accordance with section 11.2.
- A de-identified UB-04 form of any fistula intervention will be and uploaded to the eCRF.

7.10 24 Months - ± 1 month follow-up

Fistula will be assessed for maturation and patency. The following examinations will be performed:

- Doppler US:
 - [REDACTED]
[REDACTED]
 - [REDACTED]
[REDACTED]

Document title:
VasQ FDA pivotal Protocol

Document No.
CD0121

Revision
12.0
14 March 2021

Page
24 of 42

- A de-identified DICOM file of the US scan will be uploaded to a central system provided by Medical Metrics Inc. (MMI). Instructions for submitting images to MMI are provided in the Image Transfer Protocol and section 11.3.
- Physical examination including:
 - Palpation for thrill.
 - Listening for bruit by stethoscope.
 - Documentation of non-thrombotic access events: steal, infection, aneurysm, and seroma (per definitions in section 6.4).
- -
 -
 -
 -
 -
 -
 -
 -
- Dialysis status (start/stop dates, dialysis access, number and length of weekly sessions).
- Document any access intervention (type, date, purpose [initiating vs. maintenance of dialysis], outcome).
- Adverse events / Serious Adverse Events will be recorded in accordance with section 8.
- Concomitant medications update will be recorded in accordance with section 11.2.

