8 ADVERSE EVENTS

8.1 Follow-up

Throughout the course of the study adverse events will be followed and recorded as follows:

- All Adverse Events (AEs) will be followed from date of informed consent until the date of the "1 month" visit and recorded in the CRF (excluding events as detailed in section 8.4).
- Assessment of occurrence and severity of the following non-thrombotic access adverse events (per definitions in section 6.4): steal, infection, aneurysm, and seroma will be recorded during each on-site follow-up visit (1, 3, 6, 12, 24 Months visits).
- All other fistula related adverse events will be recorded in each on-site follow-up visit (1, 3, 6, 12, 24 Months visits).
- Serious adverse events (SAEs) will be followed throughout the duration of the study from date of informed consent until date of "24 months" visit or "End of study".

Document title: VasQ FDA pivotal Protocol	Document No. CD0121	Revision 12.0 14 March 2021	Page 27 of 42
--	------------------------	-----------------------------------	------------------

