10.6 Statistical analysis

10.6.1 Overview

The data will be summarized in tables listing the mean, standard deviation, median, minimum, maximum and number of subjects for continuous data, or in tables listing count and percentage for categorical data where appropriate. Data listing by subject will be provided.

All statistical analyses will be performed and data appendixes will be created using the SAS® system, Version 9.2 or higher. The effects of noncompliance, dropouts, and possible covariates such as age, gender, and center, will be assessed to determine the impact on the general applicability of results from this study.

Safety and subject disposition analyses will be done on the safety analysis set. Primary effectiveness analyses will be done on FAS_primary and PP. Secondary [REDACTED] will be tested on FAS_secondary and PP. Primary and secondary [REDACTED] endpoints will be assessed hierarchically, so that the latter will be tested only if the former’s null was rejected.

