10.6.5 Safety analyses

Safety analyses will be conducted on the safety analysis set. The main safety analyses will compare descriptively between AE rates for Steal, Infection, Aneurysm and Seroma as described in section 10.2.2. That is, we will present point estimates along with Exact Binomial, two-sided, 95% confidence intervals for each of these events separately for both our study and Schinstock et al.

Additionally, descriptive statistics will be provided, with SAE's and AE's coded by body system, preferred term, arm, severity, relation to procedure by arm and outcome. Rate of freedom from major device-related adverse events will be provided along with associated two-sided 95% Exact Binomial confidence intervals.

In addition to the dichotomously scored endpoints we will also present frequency and percent for grade for steal (mild; moderate; severe), infection (resolved with antibiotic; loss of AV; loss of limb) and seroma (resolved without treatment; aspirated, surgical treatment; loss of AV access).

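### Steal, infection, aneurysm and seroma have planned rates with exact 95% intervals only to month 6, although the same events are recorded at 12 and 24 months

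*Combined protocol and SAP*

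**What the plan says.** The synopsis sets the window: "The main safety endpoints are occurrence of the following non-thrombotic safety events at up to 6 months". Section 6.2.1 repeats it ("occurrence of the following clinically meaningful safety events at up to 6 months") and scores each event 0 or 1 per subject. Section 10.6.5 then plans "point estimates along with Exact Binomial, two-sided, 95% confidence intervals for each of these events separately", for this study and for the historical comparator, and refers back to section 10.2.2 for the method. It does not restate 6 months. The limit comes from the endpoint definition and from that cross-reference, because the comparator data in section 10.2.1 run to 6 months.

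Collection continues beyond that. Section 8.1 says that "steal, infection, aneurysm, and seroma will be recorded during each on-site follow-up visit (1, 3, 6, 12, 24 Months visits" and sections 7.9, 7.10 and Table 7-1 repeat this for the 12- and 24-month visits, under the same section 6.4 definitions.

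Three planned outputs can contain later events:
- Coded AE and SAE summaries, which under section 10.6.1 are "tables listing count and percentage for categorical data where appropriate".
- Grade tables: "we will also present frequency and percent for grade for steal (mild; moderate; severe", with similar tables for infection and seroma. Aneurysm has no grades in section 6.4 and no grade table.
- "Rate of freedom from major device-related adverse events will be provided along with associated two-sided 95% Exact Binomial confidence intervals".

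None of the three states a time point.

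**The concern.** The second study objective is to show that the device is safe, and subjects are followed for 2 years with it in place. Section 10.2.2 makes separate per-event rates with exact intervals the plan's own standard for judging safety. That standard is applied to the first 6 months only. For the other 18 months the reader gets counts and percentages, without an upper limit on the true rate. There is also no stated denominator and no rule for death, loss to follow-up, transplant or fistula abandonment. A late device-related harm, or reassurance that there is none, could not be read from the planned tables with its uncertainty.

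**Working it through.** **1. Is there a later estimate elsewhere?** None of the 20 secondary endpoints in section 6.3 (analysis sets in 10.6.6) names steal, infection, aneurysm or seroma. Time to secondary patency cessation, number of interventions and interventions per patient-year have no 6-month limit and carry 95% intervals under 10.6.6. A late event that ends the access or leads to an intervention can reach them, but not by event type. The device-related rate carries an interval, but it includes a late event only if that event is classed as major and device-related.

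**2. How much collection lies outside the window?** Scheduled on-site visits after discharge are at 1, 3, 6, 12 and 24 months. Two of five fall after month 6, covering 24 − 6 = 18 of 24 months.

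**3. The plan's own figures.** 116 / (1 − 0.10) = 128.9, so 129, as section 10.4 states. Section 10.2.2 gives a precision of 2% to 4% for the four rates at 116 subjects. The exact half-widths for the comparator rates are 2.9 points (1.4%, 2 events), 3.4 (2.4%, 3 events), 4.5 (5.1%, 6 events) and 5.3 (7.5%, 9 events). That mismatch is a separate matter; the present point does not depend on it.

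**4. What the missing interval would say.** The documents give no late event rate and no number assessed at 12 or 24 months. The event counts and the 90 below are therefore assumptions; 129 is the main cohort, 116 the plan's evaluable number and 15 the supplementary cohort. With no event, the exact (Clopper-Pearson) two-sided 95% upper limit is 1 − 0.025^(1/n):
- n = 129: 2.8%
- n = 116: 3.1%
- n = 90: 4.0%
- n = 15: 21.8%

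With 3 events:
- n = 129: 2.3% (0.5% to 6.6%)
- n = 116: 2.6% (0.5% to 7.4%)
- n = 90: 3.3% (0.7% to 9.4%)

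**5. Does the obvious repair work?** On-site visits are 6 and then 12 months apart, with windows of ±14 days and ±1 month, so the dating rule matters. Take a deliberately bad case: 116 subjects, no loss, true late incidence of 2.0% by month 12 and 6.0% by month 24, visits spread evenly over their windows, and every event dated to the visit that found it. Of the 98% free of the event after the 12-month visit, 4.0/98 = 4.08% have it found at the 24-month visit.
- Read at exactly month 12, half the visits have happened: 2.0% / 2 = 1.0%.
- Read at exactly month 24, with event-free subjects censored on their visit date: 1 − 0.98 × exp(−0.0408 × ln 2) = 4.7%, against 6.0%.
- Read at the end of the 24-month window with the same censoring, the risk set shrinks to nothing while events are still being found. With about 114 at risk, 0.0408 × (1/114 + … + 1) = 0.0408 × 5.32 = 0.217, and 1 − 0.98 × exp(−0.217) = 21%.
- Read at the end of each window, with subjects who complete the 24-month visit event-free carried to the window's end: 2.0% and 6.0%, as they should be.

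A simulation of this case gave 1.0%, 4.7%, 21%, and 2.0% and 6.0%. Documented onset dates would reduce the errors.

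**The case against.** The strongest reply is that the 6-month window was chosen to match the comparator, that safety is descriptive throughout, and that later events are tabulated anyway. Anyone can put an exact interval on a published count. Access-ending events also reach the secondary patency and intervention endpoints.

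Most of this stands. The window is sound for the comparison it serves. What does not follow is that later data need no estimate. A reader can compute an interval only from a count with a known window and a known number assessed, and the plan fixes neither. The patency and intervention endpoints do not separate the four events.

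Two stronger readings are tempting. The first is that late events go unreported; sections 8.1, 10.6.1 and 10.6.5 show otherwise. The second is that adjudication stops at month 6 because section 12 refers to the safety endpoints. Section 12 sets no end date and also sends all fistula failures and interventions to the committee, so the text supports only a request for confirmation.

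**Conclusion.** The point holds as a minor gap in the analysis plan: per-event rates with precision are planned for 6 of the 24 months in which these events are collected. Hypotheses, sample size, alpha and power are untouched, and no success decision depends on it.

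The conclusion rests on reading the 6-month limit in the synopsis and 6.2.1 into 10.6.5. If 10.6.5 was meant to cover 24 months, the missing window labels are the fault instead, and the same fix applies.

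The practical effect is not known. The upper limits above are illustrations at assumed counts. A reader might go further and calculate how far crude percentages understate late incidence, for example by repeating the 10% dropout every 6 months. The documents do not support that. The 10% in section 10.4 serves the 6-month primary endpoint, no later retention is given, and SAEs are also captured between on-site visits (8.1, 7.8) and by record review (7.11). The size of any loss bias is therefore unknown.

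**What to change.** Keep the 6-month rates and the literature comparison. Add to section 10.6.5, for each of the four events, in the safety set and by cohort:
- Cumulative incidence with a 95% interval through the end of the 12-month window (+14 days) and of the 24-month window (+1 month), plus the exact binomial proportion among subjects assessed or with the event.
- Events dated to documented onset, otherwise to the visit of detection.
- Censoring at the last contact at which the event could be ascertained (on-site visit, phone visit or record review). A subject who completes the 24-month visit without the event is carried event-free to the end of that window, for the reason shown in step 5.
- Death as a competing event. Subjects stay at risk after transplant or unrelated abandonment while the device remains in place and they are followed.

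State the time window on the grade, AE/SAE and device-related tables. Confirm in section 12 that these events are adjudicated through 24 months.

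The cost is SAP wording, one table and some labels, with no new visits or data fields. Committee work lengthens only if it was meant to stop at month 6. The downsides are that the later rates have no matched comparator in these documents, event dating is coarse, and intervals in the 15-subject cohort will be wide.
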